6.1.3 SAEs and DAEs

SAEs include death and non-fatal SAEs. All SAEs starting on or after the first dose date, including those starting more than 45 days after study drug discontinuation, will be included in the summaries on the safety set.

DAEs refer to AEs leading to permanent study drug discontinuation.

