5.5.8 Prohibited treatment

Patients who have met exclusion criteria for exclusionary medications will not be allowed to join the study. Once the patient has entered the study at Visit 3 and while the patient is on therapy, use of the following treatments are NOT allowed concomitantly with the study drug:

- Immunosuppressive medication (e.g. cyclosporine, azathioprine, methotrexate, cyclophosphamide, mitoxantrone, cladribine, rituximab, alemtuzumab);

- Other concomitant medications: immunoglobulins, monoclonal antibodies (including natalizumab), IFN β , glatiramer acetate, teriflunomide, dimethyl fumarate, adrenocorticotrophic hormone (ACTH).
- Class Ia (e.g. quinidine, disopyramide) or Class III (e.g. amiodarone, sotalol) anti-arrhythmics
- Heart-rate-lowering drugs (e.g.: Beta blockers); heart-rate lowering calcium channel blockers (e.g. verapamil, diltiazem or ivabradine)
- Digoxin, anticholinesteratic agents, pilocarpine

Careful planning is required if these medications are taken during the Core Phase (after the patient discontinued study drug treatment) then the patient must meet the washout exclusion criteria for these medications before entry into the Extension Phase. Washout of these medications must occur with adequate time to complete the full washout period prior to enrollment in the Extension Phase at Visit 15.

The administration of any live or live attenuated vaccine is prohibited while patients are receiving study drug and for 2 months after last dose of study drug.

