3.6 Treatments (study medication, rescue medication, other concomitant therapies)

3.6.1 Study medication

The duration (days) of intake to randomized study medication will be summarized on the SAF set by presenting the number (and percentage) of subjects taking the study medication for a minimum duration of time as specified in Table 3-3. Duration in terms of number of days as shown in the second column will be used in the summary tables. Summary statistics of duration to study medication will also be presented. The exposure to the actual study medication taken will also be presented in the pre-pubertal (Tanner staging score <2) and young subjects (<=12 years) subgroups.

Duration of study medication intake is the number of days on study drug during the study. The days when the subject does not take the study drug will be excluded. That is, duration

will exclude periods of temporary interruption of study medication. Only data from the core phase will be included. See [Section 3.8.3](#) for definition of core phase data.

For each treatment group, the patient-years calculated as (the sum of the number of days on study drug for all subjects in the group)/365.25, will also be presented.

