3.8.5 Safety data cutoff and visit windows for summaries on follow-up set

For safety summaries on the safety set, only core phase data (defined in 3.8.3) which are within 45 days (5 times the half-life of FTY720, 9 days) after the last dose of study drug. For safety summaries on the follow-up set, all core phase data, including assessments or events more than 45 days after the last dose of study drug in core phase, will be considered.

The time-windows below will be used in summaries on the follow-up set.

- 1) Day 1 to 45 after drug discontinuation
- 2) >Day 45 after drug discontinuation

For each of the time-window, assessments collected or events started during the specified day intervals after the last dose date will be used. The last dose date defined in Section 3.8.7 will be used to determine day windows.

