5.2 Population pharmacokinetic/pharmacodynamics analysis

Population PK/PD modeling approaches will be used to relate the individual fingolimod PK parameter estimates to key efficacy measurements (MRI-related, relapse-related). A modeling plan will be prepared before final clinical database lock providing details for the proposed PK/PD analysis. This modeling plan will be prepared and executed by PMX group. The report analysis plan and the results will be provided separately.

6 Safety evaluation

Safety assessments include adverse events, bradycardia (first dose) events, laboratory tests, vital signs, ECG, pulmonary function tests, ophthalmic examinations, Tanner stages (bone x-ray), skin assessments, and C-SSRS data.

All safety data will be summarized on the SAF set. Some safety data (AEs, vital signs, labs, PFTs and C-SSRS) will also be summarized on the follow-up set by time-window (days 1 to 45 after study drug discontinuation and more than 45 days after study drug discontinuation) to assess subjects' safety after discontinuation of the study drug.

Unless otherwise specified, safety assessments in core phase (core phase data defined in section 3.8.3) more than 45 days after the study drug discontinuation will not be included in the summaries on the safety set but will be considered in the summaries on the follow-up set.

Adverse events starting before the first dose date will be excluded from the adverse event.

Details of the safety data summaries will be provided in the sections below. All safety data will also be presented in the listings.

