is calculated as the number (n) of all such events that patients experience divided by the patient years (Ny), where patient years are calculated as the sum of the number of days on study drug of all patients divided by 365.25. The occurrence of AEs per 100 patient years, which is calculated as $n/Ny*100$, will be presented.

AEs will also be summarized on the follow-up set for the following time periods defined by days relative to study drug discontinuation: days 1 to 45 after study drug discontinuation and more than 45 days after study drug discontinuation.

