6.1.4 Occurrence of SAEs and NSAEs (non-serious AEs)

For the legal requirements of ClinicalTrials.gov and EudraCT, two required tables on on-treatment adverse events which are not serious adverse events with an incidence greater than X% and on on-treatment serious adverse events and SAE suspected to be related to study treatment will be provided by system organ class and preferred term on the safety set population.

If for a same patient, several consecutive AEs (irrespective of study treatment causality, seriousness and severity) occurred with the same SOC and PT:

- a single occurrence will be counted if there is ≤ 1 day gap between the end date of the preceding AE and the start date of the consecutive AE
- more than one occurrence will be counted if there is > 1 day gap between the end date of the preceding AE and the start date of the consecutive AE

For occurrence, the presence of at least one SAE / SAE suspected to be related to study treatment / non SAE has to be checked in a block e.g., among AE's in a ≤ 1 day gap block, if at least one SAE is occurring, then one occurrence is calculated for that SAE.

The number of deaths resulting from SAEs suspected to be related to study treatment and SAEs irrespective of study treatment relationship will be provided by SOC and PT.

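### Late off-drug SAEs enter AE and risk-term rates per 100 patient-years whose numerators and denominators cover different time, and the on-treatment registry tables have no defined window

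*SAP*

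**What the plan says.** - **General cutoff.** SAP 3.8.5 limits safety-set summaries to core-phase data "within 45 days (5 times the half-life of FTY720, 9 days) after the last dose of study drug". SAP section 6 (Safety evaluation) repeats that assessments "more than 45 days after the study drug discontinuation will not be included in the summaries on the safety set", unless the SAP specifies otherwise.
- **Exception for SAEs.** SAP 6.1.3, on the safety-set summaries: "All SAEs starting on or after the first dose date, including those starting more than 45 days after study drug discontinuation, will be included".
- **SAEs are AEs.** SAP 6.1.2 defines an AE as any entry on the AE eCRF. SAP 6.1.6 lists incidence rates and occurrence rates per 100 patient-years, for AEs and for AEs meeting the risk search terms, as safety-set summaries.
- **Occurrence rate.** SAP 6.1.2 takes all such events as numerator, and "patient years are calculated as the sum of the number of days on study drug of all patients divided by 365.25". On the related duration measure, SAP 3.6.1 says: "The days when the subject does not take the study drug will be excluded".
- **Incidence rate.** In SAP 6.1.2, a patient with the event contributes time to first onset, with no cap. An event-free patient who does not enter the extension is counted to the earlier of last core dose + 45 days and the final core visit. An event-free patient who enters the extension is counted to the final core visit.
- **Registry tables.** SAP 6.1.4 requires safety-set tables of "on-treatment serious adverse events and SAE suspected to be related to study treatment will be provided by system organ class and preferred term". It does not define on-treatment.
- **Off-drug follow-up.** Patients who stop drug stay in the study (Protocol 5.5.9; SAP 4.2.1.2) on a schedule that can run to month 24 (Protocol Table 6-2). Protocol 5.5.8 foresees that they may take MS drugs that are prohibited on study treatment.

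**The concern.** A rate per patient-year can be interpreted only if its events come from the time in its denominator. Here they do not. The occurrence-rate numerator includes events during interruptions, events in the 45-day tail and, for SAEs, events in all later core follow-up. None of that time is in the denominator. The incidence rate has its own mismatch, and its direction depends on whether the event is serious and whether the patient enters the extension.

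The distortion grows with off-drug follow-up, so it can differ between arms when stopping differs. Follow-up per patient varies in this trial, which is why the SAP presents exposure-adjusted rates at all. Separately, two programmers could reasonably produce different on-treatment SAE tables for the public registries.

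**Working it through.** **The plan's own figure.** The cutoff in SAP 3.8.5 reproduces: 5 × 9 days = 45 days, or 45/365.25 = 0.1232 years. The documents give no SAE rate and no stop rate by arm, so the rest is an illustration.

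**Inputs.** Follow-up of 2 years is the Core Phase maximum (Protocol section 4). The share d who stop drug is assumed at 5%, 15% and 30%; the 15% echoes the drop-out assumption in Protocol 9.6 and is only a middle value. Also assumed: stopping at month 12, follow-up of stoppers to month 24, the same SAE rate on and off drug, and no interruptions.

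**Occurrence rate.** On-drug time per patient = 2(1 − d) + 1·d = 2 − d.
- SAEs are counted over 2 years, so the factor is 2/(2 − d).
- Non-serious AEs are counted to last dose + 45 days, so the factor is (2 − d + 0.1232d)/(2 − d).

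| d | SAE component | Non-serious component |
|---|---|---|
| 5% | 2/1.95 = 1.026 | 1.956/1.95 = 1.003 |
| 15% | 2/1.85 = 1.081 | 1.868/1.85 = 1.010 |
| 30% | 2/1.70 = 1.176 | 1.737/1.70 = 1.022 |

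**Varying the assumptions (SAE component).**
- Stop at month 6, d = 15%: 2/1.775 = 1.127. Stop at month 18: 2/1.925 = 1.039.
- Off-drug SAE rate half the on-drug rate, d = 15%: 1.925/1.85 = 1.041. Twice: 2.15/1.85 = 1.162.
- Stoppers leave after 3 months of follow-up: (2 − d + 0.25d)/(2 − d) = 1.006, 1.020 and 1.044.

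**Between arms, true ratio 1.** 5% v 15% stopping: 1.95/1.85 = 1.054. 5% v 30%: 1.95/1.70 = 1.147. Equal stopping: 1.000.

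**Overall AE occurrence rate.** Assume SAEs are 5% to 10% of AE events (not in the documents). At d = 15%, late SAEs add (1.081 − 1.010) × 0.05 to 0.10, or about 0.4% to 0.7%. A preferred-term or risk-term row made up mostly of SAEs moves by close to the SAE factor.

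**Incidence rate, SAEs, stoppers not entering the extension.** Assume 0.10 first SAEs per year and exponential times. At d = 15%:
- Events per patient: 1 − e^(−0.2) = 0.1813.
- Time, continuers: 0.85 × 0.1813/0.10 = 1.541 years.
- Time, stoppers: 0.15 × [(1.813 − 2 × 0.8187) + 0.8187 × 1.1232] = 0.15 × 1.095 = 0.164 years. The first term is time to onset, uncapped; the second is event-free time, capped at stop + 45 days.
- Rate: 0.1813/1.705 = 0.1063, a factor of 1.063.

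For d = 5% and 30% the factors are 1.020 and 1.135.

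**Incidence rate, non-serious AEs, stoppers entering the extension.** The error reverses: events stop at day 45 but event-free time runs to the final core visit. For an infrequent event, if all stoppers enter, the factor is about (2 − d + 0.1232d)/2 = 0.978, 0.934 and 0.868.

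**With one window in numerator and denominator**, the factor is 1.00 at any stop rate under the constant-rate assumption. Cutting SAEs at 45 days but keeping on-drug days as denominator would leave the non-serious column above (1.003, 1.010, 1.022).

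**The case against.** The strongest defence is that the SAP means to show every SAE. Section 6 allows exceptions to the 45-day rule and 6.1.3 states one. No SAE is hidden, and the follow-up-set tables split AEs into days 1–45 and later, so a reader can see what arose long after stopping. This stands: counting all SAEs is a defensible conservative display. It does not justify dividing them by time that excludes where they arose.

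Three stronger readings are tempting, and the documents do not support them.
- A reader might infer that SAE rates per patient-year are inflated by the full SAE factor. SAP 6.1.6 lists no such table: SAEs appear there as incidence, or as occurrence without a patient-year label. The factor applies to the serious component of the AE and risk-term rates.
- A reader might infer that 6.1.3 puts off-treatment SAEs into the on-treatment registry tables. The label in 6.1.4 can equally be read as excluding them. The text leaves a conflict; it does not state a rule.
- A reader might infer a bias against one arm. No stop rates by arm are given, so size and direction are unknown.

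Other limits also stand. Late events are bounded by the core-phase data definition and the first extension dose (SAP 3.8.3), and routine SAE reporting ends 3 months after participation stops (Protocol 7.2). Most relapses, even with hospitalisation, are recorded on the relapse eCRF rather than as SAEs (Protocol 7.2). Safety is descriptive, and Protocol 9.5.3 names only the incidence rate; the SAP adds the occurrence rate. But the incidence rate is mismatched too.

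**Conclusion.** The concern holds in this limited form and should be corrected. Followed exactly, SAP 6.1.2 and 6.1.3 produce AE and risk-term rates per 100 patient-years whose events and exposure come from different windows. Under the stated assumptions, the serious component of the occurrence rate is overstated by about 3% to 18% for 5% to 30% stopping at month 12, and by 0.6% to 4% if stoppers leave early. The incidence rate for SAEs is overstated by about 2% to 14% among patients not entering the extension, and for non-serious AEs it errs the other way among early stoppers who do enter. Overall AE rates move far less. Any between-arm effect requires stopping patterns or off-drug SAE rates that differ by arm, on which the documents give no figures. The on-treatment label in 6.1.4 is undefined and conflicts with 6.1.3.

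**What to change.** 1. **Rates in SAP 6.1.2.** For every per-patient-year rate, count events, SAEs included, from first dose to the earliest of last core dose + 45 days, final core visit or first extension dose. Use that same calendar window, interruptions included, as the occurrence-rate denominator. Use it also as the cap on incidence-rate time at risk for every patient, with or without the event and whether or not the patient enters the extension.
2. **Registry tables in SAP 6.1.4.** Define on-treatment as this window.
3. **SAEs in SAP 6.1.3.** State that the all-SAE rule does not feed the 6.1.2 rates. Keep it as a labelled display of counts and percentages without an exposure denominator, and show later SAEs also in the existing follow-up-set table for more than 45 days after stopping.

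The cost is wording in three subsections and reprogrammed event windows and denominators. No new data are needed, and no SAE is lost from the report.

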6.1.4 Occurrence of SAEs and NSAEs (non-serious AEs)

For the legal requirements of ClinicalTrials.gov and EudraCT, two required tables on on-treatment adverse events which are not serious adverse events with an incidence greater than X% and on on-treatment serious adverse events and SAE suspected to be related to study treatment will be provided by system organ class and preferred term on the safety set population.

If for a same patient, several consecutive AEs (irrespective of study treatment causality, seriousness and severity) occurred with the same SOC and PT:

- a single occurrence will be counted if there is ≤ 1 day gap between the end date of the preceding AE and the start date of the consecutive AE
- more than one occurrence will be counted if there is > 1 day gap between the end date of the preceding AE and the start date of the consecutive AE

For occurrence, the presence of at least one SAE / SAE suspected to be related to study treatment / non SAE has to be checked in a block e.g., among AE's in a ≤ 1 day gap block, if at least one SAE is occurring, then one occurrence is calculated for that SAE.

The number of deaths resulting from SAEs suspected to be related to study treatment and SAEs irrespective of study treatment relationship will be provided by SOC and PT.

6.1.5 AEs that fulfill the risk search terms by maximum severity

The Adverse events that fulfill the risk search terms (level 1 and level 2 only) for Fingolimod are summarized by the maximum severity to support RMP report.

6.1.6 Data summaries

Summaries on the SAF set by treatment group include:

[figure not shown]
- Incidence of AEs by SOC and PT
- Incidence of AEs that fulfill the risk search terms with RMP risk by risk name and level terms
- Incidence of AEs by SOC and PT and maximum severity
- Incidence of AEs related to study drug by SOC and PT
- Incidence rate of AEs per 100 patient years by SOC and PT
- Incidence rate per 100 patient years of AEs that fulfill the risk search terms with RMP risk by risk name and level terms
- Occurrence of AEs per 100 patient-years by SOC and PT
- Occurrence per 100 patient years of AEs that fulfill the risk search terms with RMP risk by risk name and level terms
- Incidence of AEs by PT
- Incidence of deaths by SOC and PT
- Incidence of non-fatal SAE by SOC and PT
- Incidence of SAEs that fulfill the risk search terms with RMP risk by risk name and level terms
- Incidence of AEs requiring study drug interruption by SOC and PT
- Incidence of AEs requiring additional therapy by SOC and PT
- Incidence of AEs leading to study drug discontinuation by SOC and PT
- Occurrence of SAEs by SOC and PT
- Occurrence of NSAEs by SOC and PT
- Incidence of AEs that fulfill the risk search terms with RMP risk by risk name, level terms (only for level 1 and level 2), and severity

[figure not shown]
Summaries on the follow-up set by treatment group include:

- Incidence of AEs by SOC and PT by time-window (days 1 to 45 after study drug discontinuation, and more than 45 days after study drug discontinuation)

6.2 Physical examinations

According to Novartis standard eCRF policy, physical examination data will not be entered in the database. Any clinical significant findings should be reported as AEs and summarized in the AE summaries and any clinical significant change from baseline will be recorded in the vital sign eCRF and summarized in the vital sign data summaries.

6.4 Vital signs

6.4.1 Vital signs measurements

According to the protocol, three sitting measurements of blood pressure (SBP and DBP) will be taken at each blood pressure assessment. At first dose monitoring, pulse, systolic and diastolic blood pressures all will be measured 3 times at the scheduled pre-dose time point.

For post-baseline assessments (not including Day 1), the blood pressure value will be the average of the non-missing values of the 3 measurements. If more than one blood pressure assessment (scheduled or unscheduled, except for the first dose or second dose or restart dose monitoring data) exists in a particular visit-window, the blood pressure value will be the average of all assessments.

6.4.2 Vital signs notable criteria

Clinical notable criteria in vital signs are summarized in Table 6-1.

6.4.3 Data summaries

The following summaries will exclude hourly vital sign data from the first dose or second dose or restart dose monitoring (first dose data discussed in Section 6.7.1).

Summaries on the SAF set by treatment group include:

- Summary statistics and changes from baseline in vital sign parameters by visit
- Frequency (%) distributions of highest SBP, DBP, and lowest pulse in pre-defined categories respectively (as specified in the table shell);
- Incidence of notable vital sign abnormalities based on the notable criteria in Table 6-1

Summaries on the FUS by treatment group include:

- Incidence of notable vital sign abnormalities based on the notable criteria in Table 6-1 will be summarized by time-window (days 1 to 45 after study drug discontinuation, and more than 45 days after study drug discontinuation)

Plots on the SAF set by treatment group include:

- Box and whisker plot of vital signs by visit

Table 6-1 Criteria for clinically notable vital signs

Vital Sign	Age group	Notable criteria	
Heart Rate	<12 years	>130 bpm or increase of ≥ 15 bpm from baseline Or	
		<70 bpm or decrease of ≥ 15 bpm from baseline	
	≥ 12 years	>120 bpm or increase of ≥ 15 bpm from baseline Or	
		<50 bpm or decrease of ≥ 15 bpm from baseline	
Systolic Blood Pressure	<12 years	≥ 125 mmHg or increase of ≥ 20 mmHg from baseline Or	
		≤ 70 mmHg or decrease of ≥ 20 mmHg from baseline	
	≥ 12 to <18 years	≥ 160 mmHg or increase of ≥ 20 mmHg from baseline Or	
		≤ 90 mmHg or decrease of ≥ 20 mmHg from baseline	
	≥ 18 years	≥ 180 mmHg or increase of ≥ 20 mmHg from baseline or	
		≤ 90 mmHg or decrease of ≥ 20 mmHg from baseline	
	Diastolic Blood Pressure	<12 years	≥ 85 mmHg or increase of ≥ 15 mmHg from baseline Or
			≤ 50 mmHg or decrease of ≥ 15 mmHg from baseline
≥ 12 to <18 years		≥ 95 mmHg or increase of ≥ 15 mmHg from baseline Or	
		≤ 50 mmHg or decrease of ≥ 15 mmHg from baseline	
≥ 18 years		≥ 105 mmHg or increase of ≥ 15 mmHg from baseline Or	
		≤ 50 mmHg or decrease of ≥ 15 mmHg from baseline	
Temperature		>38.3 °C or an absolute change ≥ 1.1 °C from baseline	

6.5 Laboratory data

The summary of laboratory evaluations will be presented for three groups of laboratory tests: Hematology, Chemistry, and Urinalysis. On presenting summary statistics, laboratory data will be grouped and displayed in an alphabetical order within the test groups and subgroups if applicable.

6.5.1 SI Units

Data summaries will be provided in SI units. The standard conversion tool (UNITCONV) will be used to convert all values in different units to SI units.

6.5.2 Clinically notable criteria

Clinically notable abnormalities criteria are summarized in Table 6-2.

All applicable post-baseline laboratory results will be checked against the respective notable criteria. For a particular notable criterion, a subject will be counted in the notable abnormal

category as long as one of the results meets the criterion. Note that a subject can be counted in both low and high abnormal categories.

For some laboratory parameters, subjects may have a character value of "<x.x" or "<x" instead of the actual numeric value which is below the lower limit of detection (LLOD). The 50% of the LLOD rule will be applied to transform a character value into a numerical value. This rule will be applied to all applicable laboratory values prior to checking against the notable criteria as well as computation of any statistics.

Table 6-2 Criteria for clinically notable abnormalities

Hematology	Less Than	Greater Than
Hemoglobin	10 g/dL	20 g/dL
Hematocrit	0.3	0.6
RBCs	3,300,000/mm ³	6,800,000/mm ³
WBCs	3000/mm ³	15,000/mm ³
Granulocytes (Poly, neutrophils)	1000 mm ³	12000/mm ³
Lymphocytes	200 mm ³	8000 mm ³
Platelets	100,000/mm ³	600,000/mm ³
Chemistry		
Glucose	70 mg/dL (fasting and random)	120 mg/dL (fasting) 200 mg/dL (random)
Calcium	7.5 mg/dL	11.6 mg/dL
Sodium	130 mEq/L	150 mEq/L
Potassium	3.0 mEq/L	5.2 mEq/L
Chloride	85 mEq/L	119 mEq/L
BUN	2 mg/dL	30 mg/dL
Creatinine	0.2 mg/dL	1.6 mg/dL
eGFR		>19% decrease from baseline
Total bilirubin	0 mg/dL	1.2 mg/dL
SGOT (AST)	0 U/L	100 U/L
SGPT (ALT)	0 U/L	110 U/L
GGT	0 U/L	120 U/L
LDH	0 U/L	500 U/L
Alkaline Phosphatase*		
10 <-13 years	42 U/L (m) / 51U/L (f)	362 U/L (m) / 332 U/L (f)
13 <- 16 years	74U/L (m) / 50 U/L (f)	390 U/L (m) / 162 U/L (f)
16 <-18 years	52 U/L (m) / 47 U/L (f)	171 U/L (m) / 119 U/L (f)
18 years and above	37 U/L (m) / (f)	116 U/L (m) / (f)
Total Protein	4.0 g/dL	9.5 g/dL
Albumin	2.5 g/dL	6.0 g/dL
Uric Acid	1.5 mg/dL	10.0 mg/dL
*Ranges according to NIH Clinical Centre [http://cclinprod.cc.nih.gov/dlm/testguide.nsf ; 10 th May 2012]		
Urinalysis clinically notable values		Abnormality
Parameter		
WBC		>5
RBC		>5
Protein		+ or greater*
Glucose		+ or greater*
* Trace should proceed +, otherwise ++ or greater		

